### **8 SPONSOR PROTOCOL/SAFETY REPORTING**

#### **8.1 DEFINITIONS**

##### **8.1.1 Adverse Event**

Any untoward medical occurrence in a patient or clinical investigation subject administered a pharmaceutical product and which does not necessarily have a causal relationship with this treatment. An adverse event (AE) can therefore be any unfavorable and unintended sign (including an abnormal laboratory finding), symptom, or disease temporally associated with the use of a medicinal (investigational) product, whether or not related to the medicinal (investigational) product (ICH E6 (R2))

##### **8.1.2 Serious Adverse Event (SAE)**

An adverse event or suspected adverse reaction is considered serious if in the view of the investigator or the sponsor, it results in any of the following:

- Death,
- A life-threatening adverse event (see Section **8.1.3**)
- Inpatient hospitalization or prolongation of existing hospitalization
  - A hospitalization/admission that is pre-planned (i.e., elective or scheduled surgery arranged prior to the start of the study), a planned hospitalization for pre-existing condition, or a procedure required by the protocol, without a serious deterioration in health, is not considered a serious adverse event.
  - A hospitalization/admission that is solely driven by non-medical reasons (e.g., hospitalization for patient or subject convenience) is not considered a serious adverse event.
  - Emergency room visits or stays in observation units that do not result in admission to the hospital would not be considered a serious adverse event. The reason for seeking medical care should be evaluated for meeting one of the other serious criteria.
- Persistent or significant incapacity or substantial disruption of the ability to conduct normal life functions
- A congenital anomaly/birth defect
- Important medical events that may not result in death, be life-threatening, or require hospitalization may be considered a serious adverse drug experience when, based upon appropriate medical judgment, they may jeopardize the patient or subject and may require medical or surgical intervention to prevent one of the outcomes listed in this definition.

### **8.1.3 Life-threatening**

An adverse event or suspected adverse reaction is considered "life-threatening" if, in the view of either the investigator or sponsor, its occurrence places the patient or subject at immediate risk of death. It does not include an adverse event or suspected adverse reaction that, had it occurred in a more severe form, might have caused death. (21CFR312.32)

### **8.1.4 Severity**

The severity of each Adverse Event will be assessed utilizing the CTCAE version 5.

### **8.1.5 Relationship to Study Product**

All AEs will have their relationship to study product assessed using the terms: related or not related.

- Related – There is a reasonable possibility that the study product caused the adverse event. Reasonable possibility means that there is evidence to suggest a causal relationship between the study product and the adverse event.
- Not Related – There is not a reasonable possibility that the administration of the study product caused the event.

### **8.1.6 Adverse Events of Special Interest (AESI)**

There are no AESI with respect to the NCI CCR Sponsor representative for this protocol.

AESI for the pharmaceutical collaborator, Genentech, include the following:

- Cases of potential drug-induced liver injury that include an elevated ALT or AST in combination with either an elevated bilirubin or clinical jaundice, as defined by Hy's law:

- Treatment-emergent ALT or AST > 3 x ULN in combination with total bilirubin > 2 x ULN
- Treatment-emergent ALT or AST > 3 x ULN in combination with clinical jaundice
- Data related to a suspected transmission of an infectious agent by the study drug (STIAMP), as defined below:
- Any organism, virus, or infectious particle (e.g., prion protein transmitting transmissible spongiform encephalopathy), pathogenic or non-pathogenic, is considered an infectious agent. A transmission of an infectious agent may be suspected from clinical symptoms or laboratory findings that indicate an infection in a patient exposed to a medicinal product. This term applies only when a contamination of the study drug is suspected.

#### 8.1.6.1 Venetoclax-specific AESI

- Tumor Lysis Syndrome (irrespective of seriousness)

##### 8.1.6.1.1 Obinutuzumab-specific AESI

- All Tumor Lysis Syndrome (irrespective of seriousness, causality or severity)
- Second Malignancies

## 8.2 ASSESSMENT OF SAFETY EVENTS

AE information collected will include event description, date of onset, assessment of severity and relationship to study product and alternate etiology (if not related to study product), date of resolution of the event, seriousness and outcome. The assessment of severity and relationship to the study product will be done only by those with the training and authority to make a diagnosis and listed on the Form FDA 1572 as the site principal investigator or sub-investigator. AEs occurring during the collection and reporting period will be documented appropriately regardless of relationship. AEs will be followed through resolution.

SAEs will be:

- Assessed for severity and relationship to study product and alternate etiology (if not related to study product) by a licensed study physician listed on the Form FDA 1572 as the site principal investigator or sub-investigator.
- Recorded on the appropriate SAE report form, the medical record and captured in the clinical database.
- Followed through resolution by a licensed study physician listed on the Form FDA 1572 as the site principal investigator or sub-investigator.

For timeframe of recording adverse events, please refer to section [6.1](#). All serious adverse events recorded from the time of first investigational product administration must be reported to the sponsor with the exception of any listed in section [8.4](#).

## 8.3 REPORTING OF SERIOUS ADVERSE EVENTS

Any AE that meets protocol-defined serious criteria or meets the definition of Adverse Event of Special Interest that require expedited reporting must be submitted immediately (within 24 hours of awareness) to OSRO Safety using the CCR SAE report form. Any exceptions to the expedited reporting requirements are found in Section [8.4](#).

All SAE reporting must include the elements described in [8.2](#).

SAE reports will be submitted to the Center for Cancer Research (CCR) at: [[contact]](mailto:[contact]) and to the CCR PI and study coordinator. CCR SAE report form and instructions can be found here: <https://ccrod.cancer.gov/confluence/display/CCRCRO/Forms+and+Instructions>.

Following the assessment of the SAE by OSRO, other supporting documentation of the event may be requested by the OSRO Safety and should be provided as soon as possible.

#### **8.4 WAIVER OF EXPEDITED REPORTING TO CCR**

As death/hospitalization due to disease progression are part of the study objectives (DOR, PFS) and captured as an endpoints in this study, they will not be reported in expedited manner to the sponsor. However, if there is evidence suggesting a causal relationship between the study drug and the event, report the event in an expedited manner according to Section [8.3](#).

#### **8.5 SAFETY REPORTING CRITERIA TO THE PHARMACEUTICAL COLLABORATORS**

Reporting to Gilead Sciences, Inc., and Genentech, Inc., will be per the respective collaborative agreements.

#### **8.6 REPORTING PREGNANCY**

All required pregnancy reports/follow-up to OSRO will be submitted to: [[contact]](mailto:[contact]) and to the CCR PI and study coordinator. Forms and instructions can be found here: <https://ccrod.cancer.gov/confluence/display/CCRCRO/Forms+and+Instructions>

##### **8.6.1 Maternal exposure**

If a patient becomes pregnant during the course of the study, the study treatment should be discontinued immediately, and the pregnancy reported to the Sponsor no later than 24 hours of when the Investigator becomes aware of it. The Investigator should notify the Sponsor no later than 24 hours of when the outcome of the Pregnancy become known.

Pregnancy itself is not regarded as an SAE. However, congenital abnormalities or birth defects and spontaneous miscarriages that meet serious criteria (Section [8.1.2](#)) should be reported as SAEs.

The outcome of all pregnancies should be followed up and documented.

##### **8.6.2 Paternal exposure**

Male patients should refrain from fathering a child or donating sperm from the first dose until 90 days after the last dose of magrolimab, 30 days after the last dose of venetoclax, 6 months after the last dose of obinutuzumab or whichever is later.

Pregnancy of the patient's partner is not considered to be an AE. The outcome of all pregnancies occurring from the date of the first dose until 90 days after the last dose of magrolimab, 30 days after the last dose of venetoclax, and 6 months after the last dose of obinutuzumab or whichever is later should, if possible, be followed up and documented. Pregnant partners may be offered the opportunity to participate in an institutional pregnancy registry protocol (e.g., the NIH IRP pregnancy registry study) to provide data about the outcome of the pregnancy for safety reporting purposes.

#### **8.7 REGULATORY REPORTING FOR STUDIES CONDUCTED UNDER CCR-SPONSORED IND**

Following notification from the investigator, CCR, the IND sponsor, will report any suspected

adverse reaction that is both serious and unexpected. CCR will report an AE as a suspected adverse reaction only if there is evidence to suggest a causal relationship between the study product and the adverse event. CCR will notify FDA and all participating investigators (i.e., all investigators to whom the sponsor is providing drug under its INDs or under any investigator's IND) in an IND safety report of potential serious risks from clinical trials or any other source, as soon as possible, in accordance to 21 CFR Part 312.32.

All serious events will be reported to the FDA at least annually in a summary format.

## **8.8 SPONSOR PROTOCOL DEVIATION REPORTING**

A Protocol Deviation is defined as any noncompliance with the clinical trial Protocol, Manual of Operational Procedures (MOP) and other Sponsor approved study related documents, GCP, or protocol-specific procedural requirements on the part of the participant, the Investigator, or the study site staff inclusive of site personnel performing procedures or providing services in support of the clinical trial.

It is the responsibility of the study Staff to document any protocol deviation identified by the Staff or the site Monitor in the CCR Protocol Deviation Tracking System (PDTs) online application. The entries into the PDTs online application should be timely, complete, and maintained per CCR PDTs user requirements.

In addition, any deviation to the protocol should be documented in the participant's source records and reported to the reviewing IRB per their guidelines. OSRO required protocol deviation reporting is consistent with E6(R2) GCP: Integrated Addendum to ICH E6(R1): 4.5 Compliance with Protocol; 5.18.3 (a), and 5.20 Noncompliance; and ICH E3 16.2.2 Protocol deviations.

## **9 CLINICAL MONITORING**

Clinical site monitoring is conducted to ensure:

- that the rights of the participants are protected;
- that the study is implemented per the approved protocol, Good Clinical Practice and standard operating procedures; and
- the quality and integrity of study data and data collection methods are maintained.

Monitoring for this study will be performed by NCI CCR Office of Sponsor and Regulatory Oversight (OSRO) Sponsor and Regulatory Oversight Support (SROS) Services contractor. Clinical site monitoring activities will be based on OSRO standards, FDA Guidance E6(R2) Good Clinical Practice: Integrated Addendum to ICH E6(R1) March 2018, and applicable regulatory requirements.

Details of clinical site monitoring will be documented in a Clinical Monitoring Plan (CMP) developed by OSRO. CMPs will be protocol-specific, risk-based and tailored to address human subject protections and integrity of the study data. OSRO will determine the intensity and frequency of monitoring based on several factors, including study type, phase, risk, complexity, expected enrollment rate, and any unique attributes of the study and the site. The Sponsor will conduct a periodic review of the CMP to confirm the plan's continued appropriateness. A change to the protocol, significant or pervasive non-compliance with GCP, or the protocol may trigger CMP updates.

OSRO SROS Monitoring visits and related activities will be conducted throughout the life cycle of each protocol. The first activity is before the study starts to conduct a Site Assessment Visit (SAV) (as warranted), followed by a Site Initiation Visit (SIV), Interim Monitoring Visit(s) (IMVs), and a study Close-Out Visit (COV).

Some monitoring activities may be performed remotely, while others will occur at the study site(s). Monitoring visit reports will describe visit activities, observations, and associated action items or follow-up required for resolution of any issues, discrepancies, or deviations. Monitoring reports will be distributed to the study PI, NCI CCR QA, CCR Protocol Support Office, coordinating center (if applicable), and the Sponsor regulatory file.

The site Monitor will inform the study team of any deviations observed during monitoring visits. If unresolved, the Monitor will request that the site Staff enter the deviations in the CCR Protocol Deviation Tracking System (PDTs) for deviation reporting to the Sponsor and as applicable per institutional and IRB guidance.

## **10 STATISTICAL CONSIDERATIONS**

### **10.1 STATISTICAL HYPOTHESIS**

#### **10.1.1 Primary Endpoint**

- To determine the safety and tolerability of the triplet combination of venetoclax, magrolimab and obinutuzumab in relapsed and refractory indolent B-cell malignancies

#### **10.1.2 Secondary Endpoints**

- Overall response rate (ORR = CR+PR) after triplet combination therapy with magrolimab, obinutuzumab, and venetoclax
- Complete molecular remission rate (CMR) by flow cytometry or similar assays as they become available in patients after triplet combination therapy with magrolimab, obinutuzumab, and venetoclax (in CLL patients only)
- Duration of response (DOR)
- Event-free survival (EFS)
- Progression-free survival (PFS)
- Overall survival (OS)

### **10.2 SAMPLE SIZE DETERMINATION AND STATISTICAL PLAN**

The primary endpoint of this trial is to determine the safety and tolerability of the combination of magrolimab and obinutuzumab with venetoclax. We will be assessing this endpoint by using a venetoclax dose-finding scheme. During dose-finding, patients will receive magrolimab and obinutuzumab at fixed doses, and venetoclax will be administered at DL1. If required, dose de-escalation of venetoclax will be explored. Patients will be enrolled in two cohorts for this evaluation: follicular lymphoma (FL) in Cohort 1, marginal zone lymphoma (MZL), chronic lymphocytic leukemia (MCL), and mantle cell lymphoma (CLL) in the Cohort 2. Unless dose de-escalation is required, 6 total patients will be enrolled from Cohort 1 into Arm 1, and 6 total patients will be enrolled from Cohorts 2 into Arm 2. Both Cohorts 1 and 2 will include a single dose de-escalation DL(-1) if needed. A maximum of 6 treated patients will be needed to complete the dose de-escalation scheme (if required) for Cohort 1, Arm 1, and a maximum of 6 treated patients will

be needed to complete the dose de-escalation scheme (if required) for Cohort 2, Arm 2 (total 24 patients).

At the MTD of venetoclax, dose expansion cohorts will enroll patients to assess the secondary clinical response outcomes in a preliminary fashion. The dose expansion cohorts (Cohorts 3, 4, 5 and 6), based on the results of dose-escalation in Cohorts 1 and 2, will open to accrue up to 18 additional FL patients, 6 additional MZL patients, 12 additional MCL patients and 6 additional CLL patients. These numbers were chosen based on the expected number of patients which could be accrued in two years after completion of the dose-finding phase. A total of 42 treated patients will be required to complete the dose expansion phase of the study.

Based on these estimates, up to 24 patients may be required for venetoclax dose-finding. These, in addition to 42 total treated patients required to complete the dose expansion phase brings the total number of patients required to complete the study to 66. To allow for a small number of inevaluable patients and screen failures, the accrual ceiling will be set at 76 patients. It is expected that 3 to 4 years may be required to complete accrual, including dose-finding and expansion cohorts. Patients enrolled in dose-finding cohorts who are treated at the same dose-level as the expansion cohorts may be analyzed together with the dose-expansion cohorts at the end of the study (Cohort 1 with Cohort 3, and Cohort 2 with Cohorts 4, 5 and 6, respectively).

As mentioned earlier in Section [1.2.6.2.1.2](#), recent reports indicate that MZL patients may be at a higher risk of infection-related AEs with fatal outcome when obinutuzumab was used in combination with chemotherapy. As an early stopping rule, if  $\geq 2$  subjects have infection-related SAEs or any subject experiences a fatal infection-related AEs from the first 6 subjects on study, we will hold further enrollment, and a comprehensive safety analysis will be performed.

In addition, an early stopping rule will be implemented for all histologies, if a substantial number of patients have to discontinue therapy due to unacceptable toxicity. If at any point after the first 20 patients are enrolled, 25% or more patients have been unable to complete therapy due to unacceptable toxicity or if at any point 2 or more deaths or grade 4 hemolytic anemia events occur that are probably or definitely related to study therapy, then study enrollment for all histologies will be suspended for a formal assessment of the overall safety profile of the study design. This early stopping rule is applicable throughout the duration of the study.

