## **1.2 BACKGROUND AND RATIONALE**

### **1.2.1 Trial Design Summary**

This study will evaluate the safety and efficacy of magrolimab added to venetoclax and obinutuzumab in patients with relapsed and/or refractory indolent B-cell malignancies. The first portion of the study will determine the dose of venetoclax to be used during expansion. The triplet combination will use a 5-week safety ramp-up of venetoclax in patients with mantle cell lymphoma (MCL), marginal zone lymphoma (MZL), and chronic lymphocytic leukemia (CLL). Patients with follicular lymphoma (FL) will have venetoclax started at the target dose without a ramp-up. Patients without DLT in the dose-finding portion will be treated with an additional 5 cycles of triplet combination therapy.

After the dose finding portion is complete and the dose of venetoclax is known, further expansion cohorts will test the efficacy of the triplet combination within individual histologies. In the expansion phase of the study, patients will first receive a “window” of two cycles of magrolimab and obinutuzumab in order to define the early indicators of efficacy of this combination in indolent B-cell malignancies. The primary translational endpoints will occur during this window, including the molecular and immunologic correlates of response and mechanisms of resistance. After the window, venetoclax will be added. Patients who achieve CR after 6 cycles of the triplet combination will stop therapy and initiate active surveillance with periodic standard imaging and research assays for ctDNA. Patients with PR after the initial 6 cycles of the triplet combination will continue for an additional 6 cycles before stopping therapy and initiating active surveillance. Patients who do not achieve at least PR after the initial 6 cycles of the triplet combination or those who discontinue treatment before 6 cycles will stop therapy and initiate active surveillance.

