| Pyrexia             | 1 (6)  | 3 (14)  | 6 (7)                            |
| Fatigue             | 5 (28)                                       | 8 (36)  | 23 (26)                          |
| $\geq$ grade 3 AEs  | 4 (22)                                       | 9 (41)  |                                  |
| IRR                 | 0 (0)  | 2 (9)   | 10 (11)                          |
| Neutropenia         | 0 (0)  | 3 (14)  | 3 (3)                            |
| Febrile neutropenia | 0 (0)  | 1 (5)   | 0 (0)                            |
| Thrombocytopenia    | 0 (0)  | 1 (5)   | 0 (0)                            |

Recent data suggests that patients with MZL may be more susceptible to infections from obinutuzumab combinations than combinations including rituximab[\(63\)](#). In a recent Phase 3 study, obinutuzumab was evaluated in combination with CHOP (cyclophosphamide, doxorubicin, vincristine, and prednisone); bendamustine; or cyclophosphamide (C), vincristine (V), and prednisone (P) in patients with previously untreated advanced FL and chemo-naïve advanced MZL.[\(64\)](#) The MZL cohort included a higher percentage of patients in the G-chemo arm, compared with the R-chemo arm who experienced fatal AEs, Grade 3-5 AEs, SAEs and AEs leading to dose interruption and that the higher rate was due to a higher incidence of AEs with fatal outcome in the G-chemo MZL population (11.9%, compared with 4.0% for the FL population). The higher number of AEs primarily reflected significantly higher rate of infections. It is currently unknown if obinutuzumab is associated with a higher rate of infections, including opportunistic infections, in chemotherapy-free combinations. However, to maximize safety monitoring, all MZL patients will receive prophylaxis to prevent *pneumocystis jiroveci* pneumonia and will include early stopping rules for this cohort (see [Section 10.4](#)).

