#### **2.3.2.1 Cohorts**

| Number | Name   | Description  |
|---------------|---|---|
| 1             | Dose-finding:
Relapsed/refractory FL                   | Patients with relapsed or refractory FL
(a minimum of 6 patients; up to 12 patients)               |
| 2             | Dose-finding:
Relapsed/refractory MZL,
MCL, and CLL | Patients with relapsed or refractory MZL, MCL and CLL
(a minimum of 6 patients; up to 12 patients) |
| 3             | Dose-expansion:
Relapsed/refractory FL                 | Patients with relapsed or refractory FL
(up to 18 patients)  |
| 4             | Dose-expansion:
Relapsed/refractory MZL                | Patients with relapsed or refractory MZL
(up to 6 patients)  |
| 5             | Dose-expansion:
Relapsed/refractory MCL                | Patients with relapsed or refractory MCL
(up to 12 patients)                                       |
| 6             | Dose-expansion:
Relapsed/refractory CLL                | Patients with relapsed or refractory CLL
(up to 6 patients)  |

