| 4      | Experimental treatment:
MZL, MCL, CLL Dose expansion | Window of magrolimab IV with a 1 mg/kg priming dose followed by 30mg/kg loading and maintenance doses + obinutuzumab IV 1000mg combination for two (2) cycles (28-day cycles, Cycles -2 and -1), then venetoclax safety ramp-up to target dose (dose determined from Arm 2) over 5 weeks (35-days, Cycle 1). Triplet combination treatment with magrolimab + obinutuzumab + venetoclax (target dose, no ramp-up) will continue for 5 additional cycles (28-days each, Cycles 2-6); further treatment will be response-adapted. |

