**Table 8: Venetoclax dose-finding rules for Arms 1 and 2**

| Number of Patients with DLT at a Given Dose Level | Dose-Finding/Dose Decision Rules   |
|---|--|
| <2 out of 6                                       | This target dose will be used in expansion phase   |
| $\geq 2$ out of 6 at DL1                          | Six (6) patients will be entered at dose level (-1).   |
| $\geq 2$ out of 6 at DL (-1)                      | Further enrollment will be stopped, and a safety analysis will be performed to determine further course of action. |

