### 3.1.2 Dose-Expansion Phase

Once safety is confirmed, expansion cohorts (Cohorts 3 and 4 and Arms 3 and 4) will be enrolled to collect additional safety information as well as disease response (Figure 5). During the dose expansion portion of the study, all patients will receive magrolimab with obinutuzumab for 2 cycles during the “window” period (i.e., Cycle -2 and Cycle -1) designed to assess for early clinical activity and correlates of response to magrolimab and obinutuzumab. The purpose of the window is to study the molecular and immunologic correlates of response to magrolimab-based therapy. It is not intended to provide complete information regarding the clinical activity of this doublet.

[figure not shown]
After completing the window, venetoclax will be added with the dose determined from the dose-finding cohorts as described above. Patients must fulfill the clinical and laboratory criteria mentioned in Table 9 below prior to addition of venetoclax. Patients with unequivocal PD during the treatment window who are tolerating therapy will be allowed to be moved immediately to the next phase (i.e., addition of venetoclax). After completion of Cycle 1, all patients will be treated with an additional five (5), 4-week cycles of triplet combination therapy (magrolimab and obinutuzumab and venetoclax). Final duration of therapy will be based on response to the first 6 cycles of triplet combination therapy. FL, MZL and MCL patients who achieve a CR and CLL patients who achieve a CR with undetectable peripheral blood MRD by flow cytometry after 6 cycles of triplet therapy will stop treatment but remain potentially eligible for an additional 6 cycles upon disease relapse provided that they still meet re-treatment criteria and the duration of CR is  $\geq$  6 months. Disease relapse is defined by conventional criteria for clinical relapse that is associated with radiographic progression. Additionally, for CLL patients, positive flow cytometry during follow-up will be considered relapsed for re-treatment. Reappearance of ctDNA is not considered disease relapse on this protocol. Patients who achieve a PR after 6 cycles of triplet combination therapy will be eligible to receive an additional 6 cycles and then will stop treatment.

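### The infection stopping rule is meant for MZL, but its trigger counts the first six subjects of any histology and does not say whose enrolment is held

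*Combined protocol and SAP*

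**What the plan says.** Section 1.2.6.2.1.2 describes more fatal and severe adverse events in MZL than in follicular lymphoma (FL) when obinutuzumab was given with chemotherapy, attributes the excess mainly to infection, and says that it is unknown whether this carries over to chemotherapy-free combinations. As a precaution, MZL patients are to receive Pneumocystis prophylaxis, and the protocol says that it "and will include early stopping rules for this cohort", pointing to Section 10.4.

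The rule itself is in Section 10.2. Its lead-in repeats the MZL infection concern and refers back to Section 1.2.6.2.1.2. The operative sentence has two triggers: at least two subjects with infection-related SAEs, "or any subject experiences a fatal infection-related AEs from the first 6 subjects on study, we will hold further enrollment". A comprehensive safety analysis then follows.

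The next paragraph of Section 10.2 adds a second rule. That one states its scope (all histologies), what is suspended (enrolment for all histologies) and how long it applies (the whole study).

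**The concern.** The sentence that staff would act on names neither the patients who are counted nor the patients whose enrolment stops. The paragraph beside it does both, so the omission is conspicuous. Investigators, the sponsor, monitors and the safety committee all work from this text, and they should not have to infer from the preceding sentence who is counted for a safety hold.

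If the sentence is followed as written, the watch promised for the histology with the suspected higher risk is over before the MZL expansion cohort opens. The other literal consequence, a hold after two infection SAEs in FL patients, is only an extra pause.

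**Working it through.** The plan gives no operating characteristics for this rule, so there is no figure to reproduce. The check is of the text and the order of enrolment.

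**1. Intended population.** Three places agree on MZL: the promise in Section 1.2.6.2.1.2, the lead-in in Section 10.2, and the contrast with the next rule, which is introduced as an addition covering all histologies. The operative sentence is the only place that does not say so.

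**2. Literal count.** Inputs:
- Section 2.3.2.1: Cohort 1 is FL only, 6 to 12 patients. Cohort 2 is "Patients with relapsed or refractory MZL, MCL and CLL", 6 to 12 patients, with no minimum for MZL. Cohort 4 is MZL expansion, up to 6 patients.
- Section 1.2.1: "After the dose finding portion is complete and the dose of venetoclax is known, further expansion cohorts will test the efficacy".
- Section 2.3.2.2, Arm 4, which includes Cohort 4: window treatment, "then venetoclax safety ramp-up to target dose (dose determined from Arm 2) over 5 weeks".
- Table 8: the decision "This target dose will be used in expansion phase" requires fewer than 2 DLTs out of 6.
- Section 3.1.2: "Once safety is confirmed, expansion cohorts" are enrolled.

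Patients enrolled before the first Cohort 4 patient: at least 6 (the Cohort 2 minimum), or at least 6 + 6 = 12 if both dose-finding cohorts must finish, as Section 1.2.1 suggests. Cohort 4 patients among the first 6 on study: 0. MZL patients of any cohort among those first 6: anywhere from 0 to 6, because nothing reserves a place for MZL.

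**3. Would the all-histology rule step in?** It needs either 2 deaths or grade 4 hemolytic anemia events judged probably or definitely related to treatment, or, once 20 patients are enrolled, 25% unable to complete therapy because of toxicity (0.25 × 20 = 5 patients). One fatal MZL infection contributes 1 death against a requirement of 2, and 1/20 = 5% against 25%. By itself it does not fire. The infection rule, in contrast, fires on one such death.

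**4. Intended reading.** Suppose that only MZL patients count, and let m be the number of MZL patients in Cohort 2 (0 to 12).
- *Who counts.* The reference in Section 1.2.6.2.1.2 to a cohort can be taken as Cohort 4, the only all-MZL cohort. The reference in Section 10.2 to subjects on study suggests every MZL patient. Under the first, the m Cohort 2 patients are outside the rule. Under the second, they fill the six places first.
- *Whose enrolment is held.* The text fits an MZL-only hold or a study-wide hold. The two questions interact. If only Cohort 4 counts and only MZL enrolment is held, a trigger reached at the sixth patient leaves no planned Cohort 4 place to hold, because the cohort is capped at six.

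**5. Cross-reference.** Sections 10.4.1 to 10.4.9 cover analyses and reporting and contain no stopping rule; Section 10.4.6 says that no interim analyses are planned. The rule is in Section 10.2.

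**The case against.** The strongest reply is that no careful reader would take the sentence out of its paragraph. The lead-in, the back-reference and the contrast with the all-histology rule leave little doubt that MZL patients are meant, and the zero in step 2 arises only if that context is ignored. This stands as to intent. It does not settle the two points in step 4, and a safety trigger should be right as written.

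The second reply is that other safeguards narrow the gap. Dose-finding accrual is staggered, with at most two patients under DLT assessment, or one after a DLT (Section 3.1.1). A treatment-related grade 4 or fatal infection in that window is not exempt from DLT; only a grade 3 infection that improves on antimicrobials is (Section 3.1.4.1). There is prophylaxis for MZL (4.1.3), guidance on serious infection (3.4.2.5), 24-hour SAE reporting (8.3), death reporting within one business day (7.3), safety committee review (7.4.2) and a general power to suspend (13.1). This also stands: a fatal infection would be escalated promptly. None of these, however, sets an infection threshold for MZL enrolment.

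A reader might also infer that the plan leaves a gap after the sixth MZL subject. The documents do not support that as a fault. Six is the rule's own limit, an early rule bounded in this way is a design choice, and the all-histology rule runs for the whole study.

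**Conclusion.** The concern holds as a wording defect in a safety rule and should be fixed. As written, 0 of the up to 6 Cohort 4 patients can be counted. As intended, two operating points are undefined, and the first affects between 0 and 12 Cohort 2 patients, depending on how many have MZL. The zero rests on the stated order of enrolment and the Cohort 2 minimum of 6; it needs no assumed event rate.

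Two stronger readings are tempting. One is that the protocol has no MZL infection rule, or that the MZL expansion cohort would go unwatched. The documents do not support this, because the rule exists, its purpose is recoverable from context, and the other safeguards apply. The other is that the fatal adverse event rates in Section 1.2.6.2.1.2 (11.9% for MZL, 4.0% for FL) measure what is lost. They do not: they are not limited to infection, they come from combinations with chemotherapy, and the protocol calls the risk without chemotherapy unknown. The wrong section number is editorial and adds nothing to the severity.

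**What to change.** Reconcile Sections 1.2.6.2.1.2 and 10.2 so that the trigger names MZL subjects, leaving both thresholds and the limit of six subjects as they are. Have the sponsor state two things in the rule: whether the six include MZL patients from dose-finding Cohort 2, and whether the hold applies to MZL enrolment only or to the whole study. The new wording should not settle the first question by accident: a phrase covering all MZL subjects on study would already include Cohort 2. As an editorial correction, change the cross-reference in Section 1.2.6.2.1.2 from 10.4 to 10.2.

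The cost is amendment text, with no new patients, visits or data. The one downside is that the chance of an enrolment pause changes, because the six subjects watched are then all MZL.
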